## 6 Clinical evaluation, laboratory tests and follow-up

### 6.1 Before treatment start

The following assessments should be done within 28 days of randomization:

- Signature of informed consent

- demographics, medical (and cancer) history
- tumor pathology report available
- Availability of FFPE tissue (1 paraffin block or 24 unstained slides minimum)
- fresh frozen tissue from participating centers

Within 14 days of randomization:

- HBV, HCV and HIV (if allowed by local legislation) serology
- laboratory tests including:
  - hematology - Hemoglobin (Hgb), hematocrit (Hct), red blood cell (RBC) count, white blood cell (WBC) count, ANC, platelet
  - Coagulation:
    - Prothrombin time (PT) or International Normalized Ratio (INR) and
    - partial thromboplastin time (PTT) or activated PTT (aPTT)
  - biochemistry - Sodium, potassium, chloride, calcium, magnesium, glucose, Urea or BUN, serum creatinine, uric acid, ALT, AST, alkaline phosphatase, total protein, albumin, and total bilirubin
  - urinalysis - protein, blood, glucose, pH; microscopic (RBC, WBC, casts) if abnormal urinalysis
- brain MRI scan with contrast after surgical resection or biopsy. The results of tumor assessments done as part of standard of care that are within the 14-day screening period do not have to be repeated if they were done at the participating site. All scans are to be uploaded on the EORTC imaging platform. For detailed acquisition parameters, see the study specific imaging guidelines.
- MMSE and Quality of life assessment (modified EORTC QLQ C30/BN20) (Appendix E and Appendix H)
- G8 geriatric screening tool (for patients aged 70 years and above)
- For participating centers, tests of objective neurocognitive function: HVLT-R, Trail Making Tests Part A & B and COWA and the MOS questionnaire on self-perceived neurocognitive function (Appendix J)

Within 7 days of randomization:

- physical examination including height, weight
- vital signs (heart rate, temperature, blood pressure)
- Karnofsky Performance Status (KPS) scale (Appendix E)
- 12-lead ECG
- baseline adverse event assessment
- ongoing medications
- For WOCBP, urine or serum pregnancy tests
- translational research:
  - Mandatory: 10 mL blood draw for plasma and 10 mL blood draw for serum
  - Optional: 10 mL blood draw for extracellular vesicles and 20 mL for PBMC; if available, fresh-frozen tissue

## 6.2 During treatment

Treatment should start within 1 week of randomization. (Delays of 48h due to drug delivery issues will not be considered a protocol deviation.)

### 6.2.1 During the 6 weeks of RT and TMZ ± MRZ

For WOCBP a pregnancy test (serum or urine) within 72 hours before start treatment.

The following assessments should be done on a weekly basis. If baseline assessments have been done within 14 days of start of treatment, they do not have to be repeated for cycle 1 week 1.

- concomitant medications and procedures
- adverse events
- hematology as in section 6.1
- Vital signs (heart rate, temperature, blood pressure)

At D1 marizomib arm only

- 12-lead ECG within 15 minutes after end of MRZ infusion.

at 4 weeks (+ 5 days)

- biochemistry and coagulation parameters as in section 6.1

On the last day of RT (but before start of maintenance treatment):

- Karnofsky Performance Status (KPS) scale
- For WOCBP, urine or serum pregnancy tests
- MMSE and Quality of life assessment (modified EORTC QLQ C30/BN20)
- For participating centers, tests of objective neurocognitive function: HVLT-R, Trail Making Tests Part A & B and COWA and the MOS questionnaire on self-perceived neurocognitive function (Appendix J)
- translational research:
  - Mandatory: 10 mL blood draw for plasma and 10 mL blood draw for serum
  - Optional: 10 mL blood draw for extracellular vesicles and 20 mL for PBMC

### 6.2.2 During TMZ maintenance ± MRZ

The following assessment should be done before every cycle start (within 3 days before)

- physical examination (including weight)
- Karnofsky Performance Status (KPS) scale (Appendix E)
- vital signs (heart rate, temperature, blood pressure)
- concomitant medications and procedures
- adverse events
- hematology as in section 6.1
- biochemistry as in section 6.1
- For WOCBP, urine or serum pregnancy tests

At Cycle 1 marizomib arm only, pharmacokinetics.

\* At Cycle 1 D 1 (first day of the first adjuvant cycle): first blood sample for pharmacokinetics immediately after end of MRZ infusion and second sample within 45 minutes after end of MRZ infusion.

\* At Cycle 1 D 8: sample within 45 minutes after end of MRZ infusion.

At Cycle 2 Day 1 marizomib arm only

- a 12-lead ECG within 15 minutes after end of MRZ infusion.

Every 8 weeks (± 7 days)

- Brain MRI scans. The first scan should occur 4 weeks post end of RT. The 8-week imaging schedule will start after this scan.  
All scans are to be uploaded on the EORTC imaging platform. For detailed acquisition parameters, see the study specific imaging guidelines.

Every 12 weeks ( $\pm$  7 days) after start of maintenance phase

- translational research:
  - Mandatory: 10 mL blood draw for plasma and 10 mL blood draw for serum
  - Optional: 10 mL blood draw for extracellular vesicles and 20 mL for PBMC

Every 16 weeks ( $\pm$  7 days)

- MMSE and Quality of life assessment (modified EORTC QLQ C30/BN20)

Every 24 weeks ( $\pm$  7 days)

- For participating centers, tests of objective neurocognitive function: HVLT-R, Trail Making Tests Part A & B and COWA and the MOS questionnaire on self-perceived neurocognitive function (Appendix J)

### **6.2.3 During Marizomib maintenance (experimental arm, after stopping TMZ maintenance)**

The following assessment should be done before every cycle start (within 3 days):

- physical examination (weight)
- Karnofsky Performance Status (KPS) scale (Appendix E)
- vital signs (heart rate, temperature, blood pressure)
- concomitant medications and procedures
- adverse events
- hematology as in section 6.1
- biochemistry as in section 6.1
- For WOCBP, urine or serum pregnancy tests

Every 8 weeks ( $\pm$  7 days), following the imaging schedule defined in section 6.2.2

- Brain MRI scans  
All scans are to be uploaded on the EORTC imaging platform. For detailed acquisition parameters, see the study specific imaging guidelines.

Every 12 weeks ( $\pm$  7 days)

- translational research:
  - Mandatory: 10 mL blood draw for plasma and 10 mL blood draw for serum
  - Optional: 10 mL blood draw for extracellular vesicles and 20 mL for PBMC

Every 16 weeks ( $\pm$  7 days)

- MMSE and Quality of life assessment (modified EORTC QLQ C30/BN20)

Every 24 weeks ( $\pm$  7 days)

- For participating centers, tests of objective neurocognitive function: HVLT-R, Trail Making Tests Part A & B and COWA and the MOS questionnaire on self-perceived neurocognitive function (Appendix J)

## 6.3 After the end of treatment (Follow-up)

### 6.3.1 End-of-Treatment Visit

The following assessment should be done ( $28 \pm 7$  days) after the last marizomib or temozolomide dosing (whether the patient has progressed or completed the full duration of planned treatment)

- physical examination (weight)
- Karnofsky Performance Status (KPS) scale (Appendix E)
- vital signs (heart rate, temperature, blood pressure)
- concomitant medications and procedures
- adverse events
- hematology as in section 6.1
- biochemistry as in section 6.1
- urinalysis as in section 6.1
- For WOCBP, urine or serum pregnancy tests
- brain MRI scan if one has not been done in the previous 4 weeks and no progression as yet been recorded

If patient has stopped treatment due to progression:

- MMSE
- For participating centers, tests of objective neurocognitive function: HVLT-R, Trail Making Tests Part A & B and COWA and the MOS questionnaire on self-perceived neurocognitive function (Appendix J)
- translational research:
  - Mandatory: 10 mL blood draw for plasma and 10 mL blood draw for serum
  - Optional: 10 mL blood draw for extracellular vesicles and 20 mL for PBMC

### 6.3.2 Post Treatment Follow-up (every 12 weeks $\pm$ 7 days)

#### 6.3.2.1 Patient has not progressed

- results of MRI scans done as part of standard of care will be collected, or done as per the study schedule of every 8 weeks (continuing on initial schedule) until disease progression.
- MMSE, Quality of life assessment (modified EORTC QLQ C30/BN20) every 16 weeks  $\pm$  2 weeks
- For participating centers, tests of objective neurocognitive function: HVLT-R, Trail Making Tests Part A & B and COWA and the MOS questionnaire on self-perceived neurocognitive function (Appendix J) every 12 weeks ( $\pm$  7 days)
- survival status
- subsequent anti-GBM regimens, and treatment outcomes

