|--|---|

|  |  |
|--|--|
|  | 
subject has completed potentially curative treatment more than 3 years prior to study entry are allowed.
 
 
• Presence of any psychological, familial, sociological or geographical condition potentially hampering compliance with the study protocol and follow-up schedule; those conditions should be discussed with the patient before registration in the trial.
 
   |
| 
Treatment
 
Test product, dose and mode of administration
 
Duration of treatment
 | 
Experimental arm: Standard radiotherapy ( RT)(60 Gy in 30 fractions over 6 weeks) + TMZ 75 mg/m^2 p.o. daily for 6 weeks (during radiotherapy) and marizomib (MRZ) dose 0.8 mg/m^2 IV at days 1, 8, 15, 29 and 36.
 
This is followed, after 4-week break, by up to 6 cycles of maintenance TMZ 150-200 mg/m^2 p.o. on days 1-5 of a 28-day cycle and up to 18 cycles of maintenance MRZ treatment (0.8 mg/m^2 IV) at days 1, 8, 15 of a 28-day cycle until disease progression, unacceptable toxicity or withdrawal of consent.
 
Standard arm: Standard radiotherapy (RT) (60 Gy in 30 fractions over 6 weeks) + TMZ 75 mg/m^2 p.o. daily for 6 weeks (during radiotherapy) then (after 4-week break) up to 6 cycles of maintenance TMZ 150-200 mg/m^2 p.o. on days 1-5 of a 28-day cycle.
 
All patients will have regular follow-up by MRI, 4 weeks after the end of radiotherapy (RT), then every 8 weeks thereafter until progression.
 
Once patients stop study treatment, they will be followed as per institution's standard.
 |

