## 4 Trial Design

This is a multicenter, randomized, controlled, open label phase III superiority trial with an early stopping rule for futility.

After signing the informed consent form and upon confirmation of the patient eligibility, patients will be randomized 1:1 to the experimental arm (addition of marizomib to the standard treatment) or the standard arm.

**Experimental arm:** Standard radiotherapy (60 Gy in 30 fractions over 6 weeks) + TMZ 75 mg/m^2 p.o. daily for 6 weeks (during radiotherapy) and marizomib (MRZ) dose 0.8 mg/m^2 IV at days 1, 8, 15, 29 and 36.

[figure not shown]
This is followed, after 4-week break, by up to 6 cycles of maintenance TMZ 150-200 mg/m^2 p.o. on days 1-5 of a 28-day cycle and up to 18 cycles of maintenance MRZ treatment (0.8 mg/m^2 IV) at days 1, 8, 15 of a 28-day cycle until disease progression, unacceptable toxicity or withdrawal of consent (see section 5.4).

Continuation of maintenance temozolomide beyond 6 cycles is not encouraged, but will not constitute a protocol violation as long as it does not exceed 12 cycles in total.

**Standard arm:** Standard radiotherapy (60 Gy in 30 fractions over 6 weeks) + TMZ 75 mg/m^2 p.o. daily for 6 weeks (during radiotherapy) then (after 4-week break) up to 6 cycles of maintenance TMZ 150-200 mg/m^2 p.o. on days 1-5 of a 28-day cycle.

Continuation of maintenance TMZ beyond 6 cycles is not encouraged, but will not constitute a protocol violation as long as it does not exceed 12 cycles in total.

**Radiotherapy** 5x per week (total dose of 60 Gy in 30 fractions)

**Temozolomide** 75 mg/m^2 p.o. for 6 weeks (during radiotherapy), followed (after a 4-week interval) by up to 6 cycles of maintenance TMZ chemotherapy 150-200 mg/m^2 p.o., days 1-5 of a 28-day cycle

**Marizomib** 0.8 mg/m^2 i.v. at days 1, 8, 15, 29 and 36 during radiotherapy, followed (after a 4-week interval) by adjuvant treatment at days 1, 8, and 15 of a 28-day cycle until disease progression, unacceptable toxicity, withdrawal of consent or up to 18 cycles post radiotherapy

All patients will have regular follow-up by MRI, 4 weeks after end of radiotherapy then every 8 weeks thereafter.

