m Brain MRI scan if one has not been done in the previous 4 weeks and no progression as yet been recorded

n At disease progression

o Frozen tissue sample will be collected at progression if the patient undergoes salvage surgery

p Results of MRI scans done as part of standard of care will be collected, or done as per the study schedule of every 8 weeks (continuing on initial schedule) until disease progression

q For all centers, MMSE every 16 weeks  $\pm$  1 week until disease progression;  
For participating centers, tests of objective neurocognitive function: HVLT-R, Trail Making Tests Part A & B and COWA and the MOS questionnaire on self-perceived neurocognitive function every 12 weeks  $\pm$  2 weeks, until disease progression

r Quality of life assessment (modified EORTC QLQ C30/BN20) every 16 weeks  $\pm$  1 week until death or lost to follow up

s G8 will be measured in all patients aged 70 years and above at baseline†.

†.For subjects on the marizomib arm, 12-lead ECG to be collected on following days and timepoints ONLY: at baseline within 7 days of randomization: on D1 of concomitant treatment within 15 minutes after end of MRZ infusion; on Cycle 2 Day 1 of adjuvant treatment after end of MRZ infusion; and as clinically indicated.

For subjects enrolled prior to the implementation of protocol version 5., 12-lead ECG on Day 1 on the subsequent two cycles of adjuvant treatment within 15 minutes after end of MRZ infusion.

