### **7.1.1.3 Schedule of disease evaluation**

The initial assessment of disease (including measurement of all target lesions) must be performed in the two weeks preceding randomization. Follow-up assessments will be performed every 8 weeks (or earlier if clinically indicated) until disease progression.

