11.3.1. Progression-free Survival

Progression-free survival will be defined as the number of days from date of randomization to the date of earliest disease progression based on Response Assessment in Neuro-Oncology (RANO) criteria (as determined by the Investigator) or to the date of death due to any cause, if disease progression did not occur (the date of progression or death or censoring - date of randomization + 1). Subjects for whom neither death nor progression have been documented will be censored at the date of the last radiological assessment that the subject was progression-free. If a subject has no post-baseline radiological assessment, then the data will be censored at the date of randomization.

Subjects with two or more missing assessments prior to a visit with documented disease progression (or death) will be censored at the last assessment where the subject was documented to be progression free. Subjects who received new anti-cancer therapy or cancer-related surgery prior to progression or death will not be censored at the last assessment where the patient was documented as progression free prior to the new anti-cancer therapy or cancer-related surgery. Censoring rules are documented in section 15.2.

The following PFS analyses will be performed at 2-sided significance level $\alpha=0.05$ for exploratory purpose. The stratified LogRank test will be applied on the PFS time to test for differences between the 2 treatment groups. The Cox's proportional hazards model stratified by the stratification factors assessed at randomization (except institution) will provide the HR (including 95% CI). Summary of associated statistics for each treatment arm (median PFS time, 6-, 12-, 18-, 24-month PFS rate estimates and estimates for every 6 months thereafter as applicable) will be displayed with 95% CI computed using the same methods as for OS, and the Kaplan-Meier curve for PFS will be presented.

Progression-free survival Kaplan-Meier estimates will be calculated and unstratified Cox's proportional hazards model will be fitted for each subgroup defined in Section 11.5 in the ITT population only. Forest Plot will be displayed with a subgroup by treatment interaction test.

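### Off-treatment MRI may follow local practice and planned control treatment ends 48 weeks before marizomib, so PFS may be assessed at different intervals by arm, and no planned analysis checks this

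*Protocol*

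**What the plan says.** Two sets of passages govern MRI in a patient who is off treatment and has not progressed.

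Passages that allow local practice:
- Protocol 6.3.2.1: "results of MRI scans done as part of standard of care will be collected, or done as per the study schedule". The sentence goes on to name the 8-week interval, kept on its original timetable up to progression. Footnote p of the table in Protocol 6.4 offers the same choice, and the schedule table in SAP 5.1 repeats it.
- Protocol synopsis, Treatment: "Once patients stop study treatment, they will be followed as per" the institution's standard.

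Passages that set 8-weekly MRI whatever the treatment status:
- Synopsis, the sentence just before that one: "All patients will have regular follow-up by MRI, 4 weeks after the end of radiotherapy (RT), then every 8 weeks thereafter until progression".
- Section 4: "All patients will have regular follow-up by MRI, 4 weeks after end of radiotherapy then every 8 weeks thereafter", with no end stated.
- Section 7.1.1.3: "Follow-up assessments will be performed every 8 weeks (or earlier if clinically indicated) until disease progression".

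Protocol 5.3 lies between the two. After a stop for a reason other than progression, tumor assessment continues per protocol, but only where possible.

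While marizomib is given alone, Protocol 6.2.3 fixes MRI at every 8 weeks. For the analysis, SAP 11.3.1 states: "The stratified LogRank test will be applied on the PFS time to test for differences between the 2 treatment groups", with a stratified Cox model for the hazard ratio. SAP 15.1 takes the progression date from the scan that showed progression. SAP 11.3.1 and 15.2 censor a progression or death that follows two or more missed assessments.

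**The concern.** Progression seen on MRI is dated at the scan that shows it, so a longer scan interval dates the same progression later. If the interval depends on being on treatment, and one arm is planned to stay on treatment much longer, the delay is not shared equally and the PFS comparison is no longer of like with like. On planned durations the control arm would be scanned less often, its progressions would be dated later, and PFS would be biased against marizomib.

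The SAP lists PFS as its key secondary endpoint (5.2.2) and measures duration of response in the same way (11.3.2). The sensitivity analyses in SAP 11.4 cover the per-protocol population and stratification by MGMT status. Neither addresses scan timing.

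**Working it through.** **The plan's own figures.** The documents give no PFS assumption, no PFS power and no standard-of-care scan interval, so there is no stated figure on this point to reproduce. The OS design does reproduce: 86.1% power in the ITT population after the futility look (stated 86%) and 80.6% in the unmethylated subgroup (stated 80.7%). Neither depends on scans.

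**Length of the gap.** From start of treatment, with 6 weeks of RT, a 4-week break and 28-day cycles:
- Control, 6 cycles: 6 + 4 + 6 × 4 = week 34.
- Marizomib, 18 cycles: 6 + 4 + 18 × 4 = week 82.
- Gap: 82 − 34 = 48 weeks, or 336 / 30.4375 = 11.0 months.
- If a control patient takes the permitted 12 TMZ cycles: 6 + 4 + 12 × 4 = week 58, and the gap is 24 weeks (5.5 months).

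**Patients exposed.** Assume exponential PFS with a median of 6 to 10 months (not in the documents). Week 34 is 34 × 7 / 30.4375 = 7.82 months, and week 82 is 18.86 months.
- Progression-free at week 34: 0.5^(7.82/6) = 41% to 0.5^(7.82/10) = 58%.
- Progression-free at week 82: 11% to 27%.
- Events between the two: about 29% to 31% of patients. Only these fall in the window where planned schedules can differ.

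**Size of the delay.** A progression found by scan is dated on average about half an interval late: 4 weeks for 8-weekly scans, 6 for 12-weekly, 8 for 16-weekly and 12 for 24-weekly. Relative to 8-weekly scanning the extra delay is about 2, 4 and 8 weeks.

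**Missed-assessment rule.** On an 8-week grid, 16-weekly scanning skips 16/8 − 1 = 1 slot, so the rule is not triggered. With 24-weekly scanning, 24/8 − 1 = 2 slots are skipped, so a progression found at the next scan is censored.

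**Simulation, true HR 1.00.** First MRI was 4 weeks after RT, then 8-weekly on treatment, with an end-of-treatment scan when the interval changes, then the off-treatment interval below. Assumptions not in the documents: median PFS 6, 7 or 10 months; 0% or 30% of events found without a scan; median 9 months from progression to death; all progression-free patients complete planned treatment; 3 years of follow-up. The simulation standard error is about 0.01.

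| Off-treatment interval | PFS HR, marizomib/control | With the two-missed rule on the 8-week grid |
|---|---|---|
| 8 weeks | 0.99–1.01 | not run |
| 12 weeks | 1.00–1.03 | not run |
| 16 weeks | 1.00–1.05 | 1.01–1.04 |
| 24 weeks | 1.02–1.07 | 1.15–1.40 |

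A second simulation kept 60% to 100% of the marizomib arm on 8-weekly scans to week 82 and cut follow-up at week 130. It gave HR 1.01–1.02 at 12 weeks, with 12-month PFS 1.9 to 3.5 points higher in control. At 16 weeks it gave HR 1.02–1.04, with 18-month PFS 2.1 to 4.4 points higher in control.

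**The case against.** The strongest reply is that a reader might infer from 6.3.2.1 that the arms are scanned on different schedules. The documents do not establish that. The clause is an either/or that ends in the 8-week schedule, and it can be read as using routine scans where they exist and the study schedule otherwise. The synopsis, section 4 and 7.1.1.3 all point to 8 weeks. This stands: different schedules are permitted, not shown.

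A reader might also infer a large bias. Under harsher assumptions, 24-weekly scans give HRs of 1.26 to 1.68. That range was not confirmed when an end-of-treatment scan and some detection without a scan were allowed for (1.15 to 1.40). The interval itself is also unlikely: Protocol 10.4.1 and SAP 13.5 place the 16-weekly HRQoL assessment after maintenance at an MRI visit, and Protocol 6.3.2 sets follow-up visits every 12 weeks. Nor can one say that the rule simply removes late control events. That needs local practice to set the scans while the 8-week grid defines what was missed. The SAP does not say which schedule counts.

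Finally, the 48 weeks is a planned maximum. Extended TMZ narrows it, and so does the lower marizomib exposure expected after the IDMC review (SAP section 3). At the 28 April 2020 cutoff follow-up was short. If the figure of 286 enrolled on 10 July 2019 in Protocol 1.1 refers to this trial, then 616 − 286 = 330 of 616 (54%) had at most 42 weeks.

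All of this limits the size. It does not remove the conflict between the passages, and no planned table or analysis would show whether the intervals differed.

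**Conclusion.** The point holds as a permitted, arm-dependent scan interval that the SAP does not examine. If off-treatment scans are 8-weekly there is no bias. At 12 to 16 weeks it is small: HR about 1.00 to 1.05 against marizomib, with milestone PFS shifted by roughly 2 to 4 points. It becomes material (HR 1.15 to 1.40) only at about 24 weeks, with the missed-assessment rule counted on the 8-week grid. These figures rest on exponential PFS, the assumed medians and planned treatment durations; the actual local intervals are unknown.

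OS, alpha and power are untouched. PFS is tested at an exploratory two-sided 5% level, and a bias in this direction would not create a false benefit. The effect matters mainly in the long-term follow-up analysis, where events after week 34 accumulate. This is a cheap improvement, not a threat to the trial's conclusion.

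**What to change.** - **Protocol.** Reconcile the synopsis, section 4, 5.3, 6.3.2.1, footnote p and 7.1.1.3 so that one MRI schedule, independent of arm and treatment status, applies until progression. The schedule need not be re-anchored: 6.2.2 already counts from the scan 4 weeks after RT, and recruitment is closed.
- **SAP 15.2.** State which schedule defines a missed assessment for a patient on standard-of-care scans.
- **SAP 11.3.1 and 11.4.** Add a table of observed scan intervals by arm, on and off treatment. Add one supportive stratified interval-censored proportional-hazards analysis of PFS, with progression placed between the last progression-free scan and the scan showing progression, and death taken as exact. Qualify the PFS result if the two analyses differ.

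The SAP changes cost one table and one analysis on data already collected. With recruitment closed, they are the part that matters most. If the intervals turn out equal, the table shows it and the question is closed.
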